2.2* ✓	Reason visit was missed [Reason visit was missed]	[MISSREA] [A:1]  Unable to contact subject after repeated attempts [A:2]  Unable to schedule visit within the window [A:3]  Subject is early discontinued (early termination) [A:4]  Subject is hospitalized [A:5]  Subject is deceased [A:6]  [MISSSPEC] Other, please specify. A200*
2.3 ✓	Comment [Comment]	[MISSCOM] A200*
Key: [ ✓ ] = Source verification required [ * ] = ASCII Only Note: Source verification critical settings made in InForm will override any settings made in Central Designer.		

Study Object Descriptions: MISSED VISIT FORM		
Type	RefName	Description
Form	MISSFORM	MISSED VISIT FORM
Section	ScMISSEDEVISITFORM	MISSED VISIT FORM

RDE Analytics: RD_MISSFORM		
Data Variable RefName	RD Column Name	Column Data Type
MISSYN	MISSYN_C	VARCHAR2
	MISSYN	VARCHAR2
	MISSYN_ND	VARCHAR2
*RD_MISSFORM_SCMISSEDEVISITFORM		
MISSDAY	MISSDAY_C	VARCHAR2
	MISSDAY	VARCHAR2
	MISSDAY_ND	VARCHAR2
MISSREA	MISSREA_C	VARCHAR2
	MISSREA	VARCHAR2
	MISSREA_ND	VARCHAR2
MISSREA - MISSSPEC	MISSSPEC	VARCHAR2
MISSCOM	MISSCOM	VARCHAR2
	MISSCOM_ND	VARCHAR2
Key: [ * ] = The column and/or table name in the actual RDE extract may be different.		

IVACFLU-S-0203: REPORT OF PREGNANCY (REPORT OF PREGNANCY) [PREGRPT]		
REPORT OF PREGNANCY [scPREGRPT]		
1.* ✓ Pregnancy test date [Pregnancy test date]	[PREGDATE] Req  / Req  / Req  (2017-2018)	
2.* ✓ Date of last menstrual period [Date of last menstrual period]	[MENSDATE] Req  / Req/Unk  / Req  (2017-2018)	
3.* ✓ Estimated date of delivery [Estimated date of delivery]	[DELIDATE] Req  / Req/Unk  / Req  (2017-2018)	
4.* ✓ 1, Pregnancy History: [Pregnancy History:]	[NewCompound] [PREGBEFO] 1.1, Has the woman been pregnant before? [A:1]  [ANOMALY] Yes 1.2, Any history of fetal anomalies? [A:1]  Yes [A:2]  No [PREMATUR] 1.3, Any history of premature births? [A:1]  Yes [A:2]  No [DEATH] 1.4, Any history of fetal deaths? [A:1]  Yes [A:2]  No [STILLBRT] 1.5, Any history of still births? [A:1]  Yes [A:2]  No [MISCARRY] 1.6, Any history of miscarriage? [A:1]  Yes [A:2]  No [PREGOTH] 1.7 Other problem? [A:1]  [PREGSPEC] Yes, Specify: A200 * [A:2]  No [A:2]  No, Skip To 2	
5.* ✓ 2, Were there any medications taken during the time of conception or during the pregnancy? [Medications taken]	[PREGMED] [A:1]  Yes, Please complete Concomitant Medications form [A:2]  No	
6.* ✓ 3, Any additional information? [Any additional information?]	[ADDINFO] [A:1]  [PREGDESC] Yes Describe: A200 * [A:2]  No	
7.* ✓ Is subject willing to be contacted after delivery? [ Is subject willing to be contacted after delivery? ]	[PREGCONT] [A:1]  Yes [A:2]  No	
Key: [*] = Item is required [ ✓ ] = Source verification required [*] = ASCII Only Note: Source verification critical settings made in InForm will override any settings made in Central Designer.		

Study Object Descriptions: REPORT OF PREGNANCY		
Type	RefName	Description
Form	PREGRPT	REPORT OF PREGNANCY
Section	scPREGRPT	REPORT OF PREGNANCY

RDE Analytics: RD_PREGRPT		
Data Variable RefName	RD Column Name	Column Data Type
PREGDATE	PREGDATE	DATE
	PREGDATE_DTS	VARCHAR2
	PREGDATE_ND	VARCHAR2
MENSDATE	MENSDATE	DATE
	MENSDATE_DTS	VARCHAR2
	MENSDATE_DTR	VARCHAR2
	MENSDATE_ND	VARCHAR2
DELIDATE	DELIDATE	DATE
	DELIDATE_DTS	VARCHAR2
	DELIDATE_DTR	VARCHAR2
	DELIDATE_ND	VARCHAR2
NewCompound	NEWCOMPOUND_ND	VARCHAR2
NewCompound - PREGBEFO	PREGBEFO_C	VARCHAR2
	PREGBEFO	VARCHAR2
NewCompound - ANOMALY	ANOMALY_C	VARCHAR2
	ANOMALY	VARCHAR2
NewCompound - PREMATUR	PREMATUR_C	VARCHAR2
	PREMATUR	VARCHAR2
NewCompound - DEATH	DEATH_C	VARCHAR2
	DEATH	VARCHAR2
NewCompound - STILLBRT	STILLBRT_C	VARCHAR2
	STILLBRT	VARCHAR2
NewCompound - MISCARRY	MISCARRY_C	VARCHAR2
	MISCARRY	VARCHAR2
NewCompound - PREGOTH	PREGOTH_C	VARCHAR2
	PREGOTH	VARCHAR2
NewCompound - PREGSPEC	PREGSPEC	VARCHAR2
PREGMED	PREGMED_C	VARCHAR2

	PREGMED	VARCHAR2
	PREGMED_ND	VARCHAR2
ADDINFO	ADDINFO_C	VARCHAR2
	ADDINFO	VARCHAR2
	ADDINFO_ND	VARCHAR2
ADDINFO - PREGDESC	PREGDESC	VARCHAR2
PREGCONT	PREGCONT_C	VARCHAR2
	PREGCONT	VARCHAR2
	PREGCONT_ND	VARCHAR2

**IVACFLU-S-0203: END OF STUDY (EOSFM) [EOSFM]**

**End of Study [EOSSC]**

1.\* Has the participant completed the study?  
 [Has the participant completed the study?]

**[EOSYN]**  
 [A:1]  **[EOSDT]**  
 Yes  
 Date subject completed study:  
 Req  / Req  / Req  (2017-2018)

[A:2]  **[EOSCMP]**  
 No  
**[EOSRES]**  
 Primary Reason for Subject Discontinuation:  
 [A:1]  Voluntary withdrawal  
 [A:2]  Lost to follow-up  
 [A:4]  Sponsor decision  
 [A:5]  Investigator decision  
 [A:6]  **[EOSAENUM]**  
 AE or SAE  
 If AE or SAE, please specify  
 A200\*

[A:7]  **[EOSRSNOT]**  
 Other reason (specify)  
 A200\*

**[EOSVISDT]**  
 Date of last study contact for subject Req  / Req  / Req  (2017-2018)

Key: [\*] = Item is required. [] = Source verification required. [\*] = ASCII Only  
 Note: Source verification critical settings made in InForm will override any settings made in Central Designer.

**RDE Analytics: RD\_EOSFM**

Data Variable RefName	RD Column Name	Column Data Type
EOSYN	EOSYN_C	VARCHAR2
	EOSYN	VARCHAR2
	EOSYN_ND	VARCHAR2
EOSYN - EOSDT	EOSDT	DATE
	EOSDT_DTS	VARCHAR2
EOSYN - EOSRES	EOSRES_C	VARCHAR2
	EOSRES	VARCHAR2
EOSYN - EOSAENUM	EOSAENUM	VARCHAR2
EOSYN - EOSRSNOT	EOSRSNOT	VARCHAR2
EOSYN - EOSVISDT	EOSVISDT	DATE
	EOSVISDT_DTS	VARCHAR2

IVACFLU-S-0203: INVESTIGATOR SIGNATURE (SIGN) [PISIGN]	
Signature [SIGNSC]	
1. * ✓	I, the undersigned, hereby certify that I have reviewed the data of CRF and found them to be complete and accurate. [I, the undersigned, hereby certify that I have reviewed the data of CRF and found them to be complete and accurate.]
	[SIGNY] [A:1]  Yes
Key: [*] = Item is required [✓] = Source verification required Note: Source verification critical settings made in InForm will override any settings made in Central Designer.	

RDE Analytics: RD_PISIGN		
Data Variable RefName	RD Column Name	Column Data Type
SIGNY	SIGNY_ND	VARCHAR2
SIGNY - Yes	SIGNY_CITMSIGNY1_C	VARCHAR2
	SIGNY_CITMSIGNY1	VARCHAR2

InForm Special Properties For Study Design: IVACFLU-S-0203			
InForm Special Property	Property Type	Data Object RefName	Data Object Path RefName
Screening	Visit	SCRVIS	SCRVIS
Enrollment	Visit	ENRVIS	ENRVIS
Screening	Form	SYSSCR	SCRVIS.SYSSCR
Enrollment	Form	SYSEN	ENRVIS.SYSEN
Patient Identification	Form	SUBID	SCR.SUBID
Study Completion	Form	EOSFM	EOS.EOSFM
Reg Docs	Form	Unassigned	Unassigned
Visit Report	Form	Unassigned	Unassigned
Initials (Screening)	Item	SUBINI	SCRVIS.SYSSCR.SYSSCRSC.SUBINI
DOB (Screening)	Item	SCRDOBDT	SCRVIS.SYSSCR.SYSSCRSC.SCRDOBDT
Screening date (Screening)	Item	Unassigned	Unassigned
Patient No. (Enrollment)	Item	INSUBJID	SCR.SUBID.SUBIDSC.INSUBJID ENRVIS.SYSEN.SYSENRC.INSUBJID
Initials (Patient Identification)	Item	Unassigned	Unassigned
Completion status (Study Completion)	Item	EOSYN	EOS.EOSFM.EOSSC.EOSYN
Drop out reason (Study Completion)	Item	EOSRES	EOS.EOSFM.EOSSC.EOSCOMP.EOSRES
DOV (Date of Visit)	Item	DOVDT	UNSVIS.DOV1.DOVSC.DOVDT D1.DOV1.DOVSC.DOVDT SCR.DOV1.DOVSC.DOVDT Day2.DOV1.DOVSC.DOVDT Day5.DOV1.DOVSC.DOVDT D8.DOV1.DOVSC.DOVDT D22.DOV1.DOVSC.DOVDT D91.DOV1.DOVSC.DOVDT VIS5.DOV1.DOVSC.DOVDT
Randomization field (Randomization)	Item	ELIGSUBID	D1.ELIG.IE2SC.ELIGCOMP.ELIGSUBID SCR.ELIG.IE2SC.ELIGCOMP.ELIGSUBID

Personal/Protected Health Information Table: IVACFLU-S-0203		
Item RefName	Section RefName	Form RefName
No items have been defined as "Personal/Protected Health Information".		
Please note: emails sent from the trial server by the InForm application are not encrypted. If you are subject to HIPAA requirements, you should identify and block all Personal/Protected Health Information items that may be included in email notifications.		

Unit Conversions For Study Design: IVACFLU-S-0203
No unit conversion data.

Review States for Study: IVACFLU-S-0203
No Review States have been defined.

Participant ID |\_\_|\_\_|\_\_|\_\_|

### TAKE-HOME DIARY CARD

**(This part is completed by INVESTIGATOR)**

FULL NAME of participant: \_\_\_\_\_

Date of vaccination: \_\_ \_\_ / \_\_ \_\_ /2017

Vaccinated arm:       Left       Right

Date of the next visit: \_\_ \_\_ / \_\_ \_\_ /2017

Date of diary card collection: \_\_ \_\_ / \_\_ \_\_ /2017

*After reviewing the diary card completed by the participant, the investigator needs to answer the following question:*

**Does the participant have any signs and symptoms which are continuing on day 7?**

No

Yes → **Investigator to complete the form titled “Post-vaccination monitoring after day 7” and instruct the participant to monitor ongoing signs and symptoms**

FULL NAME of investigator: \_\_\_\_\_ Signature: \_\_\_\_\_

Participant ID | | | |

### TAKE-HOME DIARY CARD

[figure not shown]
#### INSTRUCTIONS

1. Take your temperature by mouth each day using the thermometer we gave you.

- Start taking your temperature later today.
- Take it around the same time each day.
- Wait 15 minutes if you had a hot or cold drink.
- Insert the thermometer into your mouth under your tongue. Close your mouth.
- Wait for the beep or other indication that the temperature is ready.
- Write the temperature in the space on the Diary Card. If you take your temperature more than once during the day, write the highest temperature for the day on the Diary Card.

2. Each day, look at your arm where you received the injection.

- Check for redness and swelling. Touch your arm and feel for hardness at the injection site.
- If you do not find anything, check “None” on the diary card for the day.
- If you see or feel something, place a mark with a pen on either side of the area. Measure the widest part of it with the ruler we have given you.
- Record your measurement on the Diary Card. If you do more than one measurement during the day, record the largest measurement for each day on the Diary Card.
- Example: This person had redness at the injection site. They put dots with a pen at the widest points of the redness and measured it. It measured 2.4 cm. They wrote 2.4 cm on the Diary Card for that day.

3. Severity of symptoms:

- None: I did not have any discomfort
- Mild: I only had minor discomfort. I did my usual activities
- Moderate: I noticed the symptom. It bothered me enough that I did not do as much as I usually do
- Severe: I really noticed the symptom. It kept me from doing many of the things I wanted or needed to do

4. Please contact the study site using the number below if you have any questions:

Participant ID | | | | |

**TAKE-HOME DIARY CARD**  
**LOCAL REACTIONS within 7 days post-vaccination**

	Evening Day 1 (Day of vaccination) ___/___/2017	Day 2 ___/___/2017	Day 3 ___/___/2017	Day 4 ___/___/2017	Day 5 ___/___/2017	Day 6 ___/___/2017	Day 7 ___/___/2017
Oral temperature	____,____ °C						
Pain at injection site	 None  Yes, grading:  Mild  Moderate  Severe	 None  Yes, grading:  Mild  Moderate  Severe	 None  Yes, grading:  Mild  Moderate  Severe	 None  Yes, grading:  Mild  Moderate  Severe	 None  Yes, grading:  Mild  Moderate  Severe	 None  Yes, grading:  Mild  Moderate  Severe	 None  Yes, grading:  Mild  Moderate  Severe
Tenderness at injection site	 None  Yes, grading:  Mild  Moderate  Severe	 None  Yes, grading:  Mild  Moderate  Severe	 None  Yes, grading:  Mild  Moderate  Severe	 None  Yes, grading:  Mild  Moderate  Severe	 None  Yes, grading:  Mild  Moderate  Severe	 None  Yes, grading:  Mild  Moderate  Severe	 None  Yes, grading:  Mild  Moderate  Severe

Participant ID | | | | |

**TAKE-HOME DIARY CARD**  
**LOCAL REACTIONS within 7 days post-vaccination**

	Evening Day 1 (Day of vaccination) ___/___/2017	Day 2 ___/___/2017	Day 3 ___/___/2017	Day 4 ___/___/2017	Day 5 ___/___/2017	Day 6 ___/___/2017	Day 7 ___/___/2017
Redness at injection site	 None  Yes, measurement: ___ mm						
Swelling at injection site	 None  Yes, measurement: ___ mm						
Hardness at injection site	 None  Yes, measurement: ___ mm						

Participant ID

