#### 10.1.1 Solicited Local and Systemic Adverse Events

- Solicited adverse events are pre-specific local and systemic adverse events that are common or known to be associated with vaccination that are actively monitored as indicators of vaccine reactogenicity. Investigators will not be required to assess causality of solicited adverse events if the onset is during the solicitation periods. If a solicited adverse event progresses beyond the solicited period, it will continue to be reported as a solicited adverse event. If the solicited adverse event occurs after the solicitation period it will be reported as an unsolicited AE.
- For this trial, solicited local and systemic AEs will be assessed by study staff 30 minutes after vaccination then daily for 7 days by the participants. Participants will be provided a thermometer, ruler and a diary to record the presence or absence of solicited AEs, severity of the solicited AE and use of concomitant medication. The severity of the solicited local and systemic adverse events will be graded using the Toxicity Table for Grading Adverse Events ([Appendix A](#)). The specific solicited local and systemic adverse events that will be reported for this trial are:
  - **Solicited local adverse event (at site of injection):**
    - Erythema / redness – based on size in cm
    - Swelling / induration (hardness at site of injection ) – based on size in cm
    - Pain

- **Systemic Reactions:**

- Fever--Body temperature
- Fatigue/malaise
- Generalized muscle aches
- Joint aches
- Chills
- Nausea
- Vomiting
- Headache

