Injection Site Erythema or Redness Report only one > 15 years of age	2.5 to < 5 cm in diameter OR 6.25 to < 25 cm  surface area AND Symptoms causing no or minimal interference with usual social & functional activities	≥ 5 to < 10 cm in diameter OR ≥ 25 to < 100 cm  surface area OR Symptoms causing greater than minimal interference with usual social & functional activities	≥ 10 cm in diameter OR ≥ 100 cm  surface area OR Ulceration OR Secondary infection OR Phlebitis OR Sterile abscess OR Drainage OR Symptoms causing inability to perform usual social & functional activities	Potentially life-threatening consequences (e.g., abscess, exfoliative dermatitis, necrosis involving dermis or deeper tissue)
Injection Site Induration or Swelling Report only one > 15 years of age	Same as for Injection Site Erythema or Redness, > 15 years of age	Same as for Injection Site Erythema or Redness, > 15 years of age	Same as for Injection Site Erythema or Redness, > 15 years of age	Same as for Injection Site Erythema or Redness, > 15 years of age

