## 2.4 ASSESSMENT OF OBJECTIVES

### 2.4.1 ENDPOINT VARIABLES

- Solicited local adverse events (at site of injection):
  - Erythema / redness - based on size in cm
  - Swelling / induration (hardness at site of injection) - based on size in cm
  - Pain

---

Document: \\EEDC-NAS01A\Biosdata\Path\IVACFLU-S\IYA06804\Biostatistics  
Documentation\SAP\IVACFLU-S-0203\_SAP\_Draft v1.0

Author: [name]

Version Number:

1.0

Version Date:

[11AUG2017]

Template No: CS\_TP\_BS016 Revision 4  
Effective Date: 01Apr2016

Reference: CS\_WI\_BS005

- Solicited systemic adverse events:
  - Fever-Body temperature
  - Fatigue/malaise
  - Generalized muscle aches
  - Joint aches
  - Chills
  - Nausea
  - Vomiting
  - Headache
- Unsolicited adverse events
- Serious adverse events
- Seroprotection
- Seroconversion
- Geometric mean titers (GMT) of serum HAI antibodies
- Geometric mean fold rises (GMFR) of serum HAI antibodies

### 2.4.1.1 PRIMARY SAFETY ENDPOINTS, PHASE 2 AND 3

The number and proportion of participants reporting the following events:

- A. Solicited local adverse events, including redness / erythema, swelling / induration, pain within 30 minutes of vaccination and over a 7-day period (Days 1-7) post-vaccination.
- B. Solicited systemic adverse events, including fever, fatigue/malaise, muscle aches, joint aches, chills, nausea, vomiting, and headache within 30 minutes of vaccination and over a 7-day period (Days 1-7) post-vaccination.
- C. Unsolicited Adverse Events (AEs) occurring within 21 days post vaccination.
- D. Serious Adverse Events (SAEs) occurring during the entire study period (Days 1-91).

### 2.4.1.2 PRIMARY IMMUNOGENICITY ENDPOINTS, PHASE 3

- A. Number and percentage of participants by age groups (18-45, 46-60) with seroconversion against each of the 3 vaccine antigens post-vaccination. Seroconversion is defined as a serum HAI antibody titer meeting the following criteria:
  - pre-vaccination titer <1:10 and a post-vaccination titer measured on Day 22 of  $\geq 1:40$  or
  - pre-vaccination titer  $\geq 1:10$  and at least a four-fold increase in post vaccination measured on Day 22

---

Document:	\\EEDC-NAS01A\Biosdata\Path\IVACFLU-S\IYA06804\Biostatistics		
	Documentation\SAP\IVACFLU-S-0203_SAP_Draft v1.0		
Author:	[name]	Version Number:	1.0
		Version Date:	[11AUG2017]
Template No:	CS_TP_BS016 Revision 4	Reference:	CS_WI_BS005
Effective Date:	01Apr2016		

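### The diary card's worked example is in centimetres but its size boxes are printed in millimetres, so a bare cm entry can push a local reaction below Grade 1, and no step checks the unit

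*Combined protocol and SAP*

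**What the plan says.** The take-home diary card asks the participant to measure the widest part of any redness, swelling or hardness with the ruler supplied. The recording step names no unit: "Record your measurement on the Diary Card". The only unit in the instructions is in the worked example: "It measured 2.4 cm. They wrote 2.4 cm on the Diary Card for that day".

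The page for local reactions within 7 days gives each of the three signs a tick for none or yes and a size box: "Yes, measurement: ___ mm". Every size box that can be read in the document is in millimetres.

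The other places that define or grade these reactions use centimetres:

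- Protocol section 10.1.1: "Erythema / redness – based on size in cm".
- SAP section 2.4.1: "Swelling / induration (hardness at site of injection) - based on size in cm".
- Appendix A, injection site erythema, which also applies to induration and swelling: Grade 1 is "2.5 to < 5 cm in diameter", Grade 2 is "≥ 5 to < 10 cm in diameter", and Grade 3 starts at 10 cm.
- The 30-minute reactogenicity form of the eCRF has size fields in cm.

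SAP section 17.2.1 says that the severity of these three signs always follows their size. The eCRF form for Days 1-7 (Solicited Local Reactogenicity) has no size field. For each day it holds one code from none to potentially life-threatening.

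**The concern.** One form gives the participant two units that differ by a factor of ten. The example leads towards 2.4 and the box asks for 24. The grading cut-points are 2.5, 5 and 10 cm, so a ten-fold slip is large enough to cross all of them.

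After the 30-minute check, the diary is the daily record of these reactions, and its numbers feed the severity grades of solicited local reactions over Days 1-7. Those reactions belong to the primary safety endpoint (protocol section 3.2.1, item A), and the Phase 2 data up to Day 8 inform the move to Phase 3. The size is turned into a code before it reaches the database, so a unit error would leave nothing there to query. Only the paper card would show it.

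**Working it through.** The plan gives no figure of its own on this point. The check has two steps: apply the grading table to a ten-fold error in each direction, then bound how many participants could be affected.

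**Step 1: effect on the grade.** Inputs: the Appendix A cut-points (below 2.5 cm no grade; 2.5 to under 5 cm Grade 1; 5 to under 10 cm Grade 2; 10 cm and over Grade 3), and 1 cm = 10 mm.

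- Case A: a cm number written in the box and read as mm. Size as read = true size / 10.
- Case B: a mm number read as cm. Size as read = true size x 10.

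| True size | True grade | Case A reads as | Case B reads as |
|---|---|---|---|
| 0.3 cm | below 1 | 0.03 cm, below 1 | 3 cm, Grade 1 |
| 0.5 cm | below 1 | 0.05 cm, below 1 | 5 cm, Grade 2 |
| 1.0 cm | below 1 | 0.1 cm, below 1 | 10 cm, Grade 3 |
| 2.4 cm | below 1 | 0.24 cm, below 1 | 24 cm, Grade 3 |
| 3 cm | Grade 1 | 0.3 cm, below 1 | 30 cm, Grade 3 |
| 7 cm | Grade 2 | 0.7 cm, below 1 | 70 cm, Grade 3 |
| 12 cm | Grade 3 | 1.2 cm, below 1 | 120 cm, Grade 3 |
| 24.9 cm | Grade 3 | 2.49 cm, below 1 | 249 cm, Grade 3 |

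In Case A, every true size from 2.5 cm to under 25 cm falls below Grade 1. Sizes under 2.5 cm have no grade to lose, and the card's own 2.4 cm example is one of these. In Case B, every true size of 1 cm or more becomes Grade 3. Case A is the more plausible: the participant follows the example's number and the reader follows the printed label. In Case B the reader has to override the label.

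**Step 2: how many could lose a grade in Case A.** Only reactions of 2.5 cm or more count. The protocol's size-graded data are in section 2.2.2, Table 11 (a licensed split-virus vaccine, adults 18 to 64). That table's Grade 2 is 2.5 to under 5 cm and its Grade 3 is 5 cm or more, so the two together give the share at or above 2.5 cm:

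- Erythema: 2.1% + 0.9% = 3.0%
- Swelling: 2.1% + 0.9% = 3.0%
- Induration: 2.3% + 0.5% = 2.8%

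The planned vaccine group is 740 (protocol section 13.3):

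- 740 x 0.030 = 22.2
- 740 x 0.028 = 20.7

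That is about 21 to 22 vaccine recipients per sign if every such reaction were misread. The share actually misread is not known. As assumptions, 10% would give about 2 per sign (22.2 x 0.10 = 2.2) and 50% about 11 (22.2 x 0.50 = 11.1).

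**The case against.** The strongest reply is that the card does carry a unit and that people look at it. The box is labelled mm, so a bare number has a stated meaning. A participant who copies the example fully writes the unit too, and the conflict is then visible. Participants are shown how to use the card and ruler on Day 1. Staff contact them on Days 2 and 5 to see that the card is being filled in properly, and a suspected Grade 3 reaction reported then brings the participant back to the clinic. Staff go through the card with the participant on Day 8, and the Day 1-7 eCRF form is completed from the card together with an interview. Most of this stands, and it lowers the risk. It does not remove it: none of these steps mentions the unit or a conversion, and the reviewer grades in cm from a box in mm.

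Four stronger readings are tempting and are not supported.

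- A reader might infer that upward and downward errors are equally likely. The printed label argues against that.
- A reader might apply reaction rates for any size, such as 18% redness in protocol Table 13, which would give 740 x 0.18 = 133. In Table 11, erythema of any size is 13.2% but only 3.0% is 2.5 cm or more, so most reactions have no grade to lose in the likelier direction.
- A reader might infer a bias specific to the vaccine arm. Recording is blinded, and the placebo rates quoted in the protocol are not far below the vaccine rates (Table 13: redness 10% against 18%, swelling 6% against 9%). Much of any imbalance in counts would come from the 5:1 allocation.
- A reader might infer that the count of participants with a reaction is corrupted. The none/yes tick on the card does not depend on the unit. How a ticked reaction under 2.5 cm is coded on the Day 1-7 form is a separate question, which arises even when the unit is right.

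**Conclusion.** The contradiction is real and can be checked on the card itself. It creates a risk to the severity grade of redness, swelling and hardness over Days 1-7, mainly towards under-grading. It is not evidence that any entry was misread. The upper bound is about 21 to 22 of 740 vaccine recipients per sign. It assumes that the licensed vaccine's size distribution applies to IVACFLU-S and that every reaction of 2.5 cm or more is entered as a bare cm number and read as mm. The true figure is likely to be lower because of the existing contacts and the Day 8 review.

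Immunogenicity and sample size are not touched. The point should still be fixed: it bears on a primary safety endpoint, the database cannot reveal the error, and the remedy costs little.

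**What to change.** Use one unit on the card. Change the size boxes for redness, swelling and hardness to the form __._ cm, so that they match the card's example, protocol section 10.1.1, Appendix A and the SAP. For cards already issued, have the Day 8 reviewer confirm the unit with the participant, write it beside each measurement, and convert to cm before assigning the grade.

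The cost is one reprinted diary page and one added line in the Day 8 review instruction. The analysis does not change.

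This change does not bring the card into line with the Day 1-7 eCRF form, which has no size field. Adding size in cm there would make grades checkable, and would be needed if the summary of reaction sizes in SAP section 17.2.1.2 is meant to cover Days 1-7. That is a database change with its own cost and can be decided separately.
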